11.2 Subject demographics and other baseline characteristics

All data for background and demographic variables will be listed by treatment group and patient. Summary statistics will be provided by treatment group, overall and for each study part separately.

Relevant medical history, current medical conditions, outcome of renal biopsy at baseline and other relevant information will be listed by treatment group and patient, overall and for each study part separately.

The FAS will be used for these analyses.

11.3 Treatments

Data for study drug administration and concomitant therapies will be summarized by treatment group, for the SAF (up to Day 90) and for SAF1 and SAF2 separately.

Total duration of time on study drug and reasons for discontinuation of study drug will be summarized by treatment group, for the SAF (up to Day 90) and for SAF1 and SAF2 separately.

11.4 Analysis of the primary variable(s)

At the final analysis, a one-sided type I error rate of 10% (2-sided type I error rate of 20%) will be used for all efficacy analyses. Correspondingly, two-sided 80% confidence intervals (CIs) will be presented.

11.4.1 Primary Variable(s)

The primary variable is the change from baseline of log transformed UPCR derived from the 24h urine collections at baseline and day 90.

11.4.2 Statistical model, hypothesis, and method of analysis

At the time of final analysis all data from Part 1 and Part 2 of the study up to day 90 will be pooled and analyzed for the primary analysis; the FAS set (up to Day 90) will be used. If the study is stopped at the end of Part 1, then the results of the interim analysis will become the final analysis results.

The primary endpoint will be analyzed using Multiple Comparison Procedure (MCP) methodology as described as part of MCP-Modelling (MCP-Mod) by [Bretz et al 2005](#) and [Pinheiro et al 2014](#).

A two stage approach will be taken for this analysis: first, change from baseline in log transformed UPCR at multiple time points will be analyzed using a Mixed Model of Repeated Measures (MMRM) model. UPCR is derived from the 24h urine collections at baseline, day 30 and 90. The results will be back transformed and presented on the original scale.

The model will include treatment, time point (as study day relative to start of study treatment), study part (Part 1 or Part 2) and ancestry (Asian/non-Asian) as fixed effects and baseline log UPCR as fixed covariate. Baseline is defined to be the last measurement prior to randomization. Treatment by time point and time point by baseline log UPCR will be included as interaction terms. Timepoint will be included as a repeated factor with an unstructured covariance matrix to allow adjustment for correlations between time points within patients.

Secondly, the following global hypothesis will be tested for the day 90 time point using the generalized MCP-Mod approach ([Pinheiro et al 2014](#)) at the one-sided 10% significance level to assess whether LNP023 is different from placebo:

$$H_0: c_m^T \mu = 0 \text{ for all } m \text{ in } \{1, \dots, 6\}$$

$$H_1: c_m^T \mu > 0 \text{ for at least one } m \text{ in } \{1, \dots, 6\}$$

where μ is the vector of adjusted means (on the log transformed scale) for each treatment group from the analysis of the primary endpoint at day 90 i.e. $\mu = (\mu_{\text{Placebo}}, \mu_{\text{LNP023 dose 1}}, \dots, \mu_{\text{LNP023 dose n}})^T$ and c_m^T is the vector of optimal contrasts coefficients for the m^{th} candidate dose response shape m , as described below.

- Model 1: Linear
- Model 2: Emax with ED50 at 5mg
- Model 3: Emax with ED50 at 50mg
- Model 4: Sigmoidal emax with ED50 at 25mg and Hill parameter=3
- Model 5: Sigmoidal emax with ED50 at 50mg and Hill parameter=3

- Model 6: Exponential with $\delta = 50$

The contrast test statistics will be calculated as standardized linear combinations of the estimated treatment effects using (i) the optimal contrast coefficients (ii) the adjusted means and variance-covariance matrix from the MMRM analysis.

The multiplicity adjusted critical value for the one-sided 10% significance level will then be determined from the joint multivariate t-distribution of the optimal contrasts using the correlation between test statistics. The hypothesis H_0 is to be rejected if the maximum of all t-statistics is larger than the derived critical value.

The dose response curve and the ED90 will be estimated together with 80% confidence intervals.

11.4.3 Handling of missing values/censoring/discontinuations

The primary analysis will include all available data up to the point of treatment discontinuation for patients who discontinue.

This method is valid and consistent under a missing at random (MAR) assumption, i.e. given the observed data (responses and covariates) the probability of drop-out does not depend on the unobserved responses.

Supportive analyses to assess the impact of any incomplete data on the results will be performed and will include all available data regardless of whether treatment was taken or not in an intention-to-treat manner. Further details will be provided in the Statistical Analysis Plan (SAP).

11.4.4 Sensitivity analyses

Sensitivity analyses aimed at assessing the sensitivity of the conclusions to the model specification will be described in the SAP.

11.5 Analysis of secondary variable(s)

11.5.1 Efficacy / Pharmacodynamics

The secondary variables supporting the secondary objective to assess the effect of LNP023 on renal function are eGFR, serum creatinine, hematuria, 24h-UP, 24h-UA, UACR,, UPCR (from first morning void). These variables will each be analyzed with the same MMRM model used for the primary variable. Appropriate transformations for each variable will be detailed in the SAP. Estimates of the differences between each dose of LNP023 and placebo will be calculated.

For eGFR, UPCR (from 24 hour sample and first morning void), hematuria and UACR, the MMRM will be repeated considering measurements up to day 180 (i.e. for FAS2 only); the MMRM for this analysis will not include the study part fixed effect term.

A further secondary analysis of UPCR after the end of treatment will be performed, for FAS1 and FAS2 separately. This analysis would also follow the MMRM approach described for the primary variable but will include UPCR measured up to the EOS.

11.5.2 Safety

Vital signs

All vital signs data will be listed by treatment, patient, and time point and abnormalities will be flagged. Summary statistics will be provided by treatment and time point, for the SAF (up to Day 90), and for SAF1 and SAF2 separately.

To assess the effect of LNP023 on blood pressure after dosing with LNP023, blood pressure and heart rate at 1-2 hours post dose on Day 1 and Day 30 (see [Assessment schedule](#)) expressed as change from baseline will be summarized, for the SAF. This represents the blood pressure at the approximate time of C_{max} after first dose and at steady state. The relationship between changes in blood pressure and heart rate and the C_{max} concentrations will also be investigated graphically.

ECG

All ECG data will be listed by treatment, patient, and time point, and abnormalities will be flagged. Summary statistics will be provided by treatment and time point, for the SAF (up to Day 90) and for SAF1 and SAF2 separately; the number of patients with values above key threshold values will be displayed.

Clinical laboratory evaluations

All laboratory data will be listed by treatment, patient and time point, and if normal ranges are available abnormalities will be flagged. Summary statistics will be provided by treatment and time point, for the SAF (up to day 90) and for SAF1 and SAF2 separately.

Adverse events

All information obtained on AEs will be displayed by treatment and patient.

The number and percentage of subjects with adverse events will be tabulated by System Organ Class (SOC) and Preferred Term (PT) with a breakdown by treatment, for the SAF (up to day 90) and for SAF1 and SAF2 separately. A subject with multiple AEs events within a SOC is only counted once towards the total of this SOC for the event of highest severity.

Exposure-adjusted AE summaries will also be likewise considered.

Summaries of SAEs will be provided in a similar manner.

Further displays of AEs may be produced in order to appropriately describe the outcomes seen in this trial.

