3.6.2.5 Non-clinical safety findings of undetermined relevance

In toxicology studies with LNP023, a few findings were observed that are considered of undetermined relevance based on current knowledge. These have not been seen in the clinical setting thus far, and there is no evidence to conclude that these have a causal association with LNP023 exposure or an impact on the risk-benefit balance of LNP023.

Cardiovascular effects: LNP023 in medium to high doses in dogs elicited peripheral vasodilatation, reducing the total peripheral resistance and blood pressure in addition to causing compensatory heart rate increase. At the highest doses, pathological changes were noted in the dogs. The response may be present in humans, even though it was not seen in other species. Small QTc effects were observed at high doses and exposures in nonhuman primates, but in no other species. The risk for humans is considered to be small, but vital signs, ECGs and cardiac AEs will be closely monitored. See [Section 8.6.7](#)

Hyperbilirubinemia: In the 4-week GLP toxicological study, a significant dose-dependent effect was observed on the conjugated bilirubin levels in rats and dogs. The effect was considered to be minimal to mild. No change was observed in liver enzymes and the effect was reversible in all animals. Increased bilirubin was accompanied by bile duct hyperplasia in one high-dose dog. At this point it is not known if the hyperbilirubinemia is translatable to humans. Liver function tests and hepatic AEs will be closely monitored in the LNP023 program. See [Section 8.6.8](#).

Proteinuria: This finding was observed in rats treated with high doses of LNP023 (1,000 mg/kg), but electron microscopy did not reveal any morphological changes. The effect was fully reversible, and morphological changes and proteinuria were not observed in dogs. Urine and renal function will be closely monitored. See [Section 8.8.4](#)

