 - Evidence of urinary obstruction or difficulty in voiding any urinary tract disorder other than IgAN that is associated with hematuria at screening and before dosing; [If necessary, laboratory testing may be repeated on one occasion (as soon as possible) prior to randomization, to rule out any laboratory error]
 7. Pregnant or nursing (lactating) women, where pregnancy is defined as the state of a female after conception and until the termination of gestation, confirmed by a positive hCG laboratory test.
 8. A history of clinically significant ECG abnormalities, or any of the following ECG abnormalities at screening or baseline:
 - PR > 200 msec
 - QRS complex > 120 msec
 - QTcF > 450 msec (males)
 - QTcF > 460 msec (females)
 - History of familial long QT syndrome or known family history of Torsades de Pointes
 - Use of agents known to prolong the QT interval unless they can be permanently discontinued for the duration of the study
 9. History of severe allergic reactions as per Investigator decision
 10. Plasma donation (> 200 mL) within 30 days prior to first dosing.
 11. Donation or loss of 400 mL or more of blood within eight (8) weeks prior to initial dosing, or longer if required by local regulation

12. Women of child-bearing potential, defined as all women physiologically capable of becoming pregnant, unless they are using effective methods of contraception from first dosing until an additional one week following cessation of study drug. *Effective contraception methods include:*

- Total abstinence from heterosexual intercourse (when this is in line with the preferred and usual lifestyle of the subject). Periodic abstinence (e.g., calendar, ovulation, symptothermal, post-ovulation methods) and withdrawal are not acceptable methods of contraception.
- Female sterilization (have had surgical bilateral oophorectomy with or without hysterectomy), total hysterectomy or tubal ligation at least six weeks before taking investigational drug. In case of oophorectomy alone, only when the reproductive status of the woman has been confirmed by follow up hormone level assessment.
- Male sterilization (at least 6 months prior to screening). For female subjects on the study the vasectomized male partner should be the sole partner for that subject.
- Barrier methods of contraception: Condom or Occlusive cap (diaphragm or cervical/vault caps). For UK: with spermicidal foam/gel/film/cream/vaginal suppository

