 - Arithmetic mean (SD) profiles of hematology parameters over time by treatment group – Part 2 patients on 180 days of treatment

- Overlaying individual time profiles (spaghetti plots) of hematology parameters by time and treatment group - Parts 1 and 2 to Day 90
 - Overlaying individual time profiles (spaghetti plots) of hematology parameters by time and treatment group – Part 2 patients on 180 days of treatment
 - Arithmetic mean (SD) profiles of reproductive hormone levels over time, by gender and treatment group – Parts 1 and 2 to Day 90
 - Arithmetic mean (SD) profiles of reproductive hormone levels over time, by gender and treatment group – Part 2 patients on 180 days of treatment
 - Arithmetic mean (SD) profiles of thyroid hormones over time by treatment group – Parts 1 and 2 to Day 90
 - Arithmetic mean (SD) profiles of thyroid hormones over time by treatment group – Part 2 patients on 180 days of treatment
 - Arithmetic mean (SD) profiles of blood pressure over time by treatment group – Parts 1 and 2 to Day 90
 - Arithmetic mean (SD) profiles of blood pressure over time by treatment group – Part 2 patients on 180 days of treatment
 - Overlaying individual time profiles (spaghetti plots) of vital signs by time and treatment group - Parts 1 and 2 to Day 90
 - Overlaying individual time profiles (spaghetti plots) of vital signs by time and treatment group – Part 2 patients on 180 days of treatment
 - Arithmetic mean (SD) of QTcF interval over time by treatment group – Parts 1 and 2 to Day 90
 - Arithmetic mean (SD) of QTcF interval over time – Part 2 patients on 180 days of treatment
 - Arithmetic mean (SD) profiles of heart rate over time by treatment group – Parts 1 and 2 to Day 90
 - Arithmetic mean (SD) profiles of heart rate over time by treatment group – Part 2 patients on 180 days of treatment
 - Number and percentage of subjects with ECG abnormalities, by treatment group and time point – Parts 1 and 2 to Day 90
 - Number and percentage of subjects with ECG abnormalities, by treatment group and time point – Part 2 patients on 180 days of treatment
 - Number and percentage of subjects with newly occurring liver enzyme abnormalities, by treatment group and time point – Parts 1 and 2 to Day 90
 - Number and percentage of subjects with newly occurring liver enzyme abnormalities, by treatment group and time point – Part 2 patients on 180 days of treatment
- Pharmacodynamic (PD) analyses include, but are not limited to:

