Data for study drug administration, corticosteroid or immunosuppressant therapy (CS/IS) (as shown in Section 13) and concomitant medication and non-drug therapies will be listed by treatment group and subject.

Concomitant medications prior to randomization will be summarized by therapeutic class, PT and treatment group for the SAF. Concomitant medications after randomization will be likewise summarized for the SAF (to Day 90), SAF1 and SAF2 separately. Use of corticosteroid or immunosuppressant therapy (CS/IS) will be summarized. Significant non-drug therapies/procedures will also be summarized by ATC class and concomitant medication category and treatment group.

A summary of compliance of vaccination by vaccine type and treatment, will be tabulated.

Vital signs

All vital signs data will be listed by treatment, subject, and visit/time and if ranges are available, abnormalities (and relevant orthostatic changes) will be flagged.

Vital signs should be within the following ranges:

- Body temperature between 35.0-37.5°C
- Systolic blood pressure between 90-160 mm Hg
- Diastolic blood pressure, 50-90 mm Hg
- Pulse rate, 40-90bpm

Summary statistics will be provided by treatment and visit/time for the SAF (up to Day 90) and for SAF1 and SAF2 separately. Summary statistics will include mean, SD, CV, Q1, median, Q3, minimum and maximum as appropriate.

To assess the effect of LNP023 on blood pressure after dosing with LNP023, blood pressure and heart rate at 1 and 2 hours post dose on Day 1, and 2 hours post dose on Day 30 expressed as change from baseline will be graphically presented by treatment, for the SAF. This represents the blood pressure at the approximate time of C_{max} after first dose and at steady state. The relationship between changes in blood pressure and heart rate, and the C_{max} concentrations will also be investigated graphically.

ECG evaluations

All ECG data (including but not limited to QTcF prolongation, QT interval and HR) will be listed by treatment, subject and visit/time and abnormalities will be flagged.

Summary statistics will be provided by treatment and visit/timepoint, for the SAF (up to Day 90) and for SAF1 and SAF2 separately, and the frequency of (n, %) patients with the following abnormalities will be displayed:

- QRS > 120 ms
- QRS increase from baseline > 25%
- QTcF > 500ms
- QTcF increase from baseline > 60 ms
- Resting heart rate sinus rhythm (HR) < 30 bpm
- HR decrease from baseline \geq 25%
- HR > 130 bpm

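### The ECG frequency table in the SAP has no PR row and no QTcF row below 500 ms except a rise above 60 ms, so moderate QTcF crossings and all PR prolongations are left out of its counts

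*Protocol*

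**What the plan says.** Protocol 11.5.2 (ECG) commits to listings with abnormalities flagged, summary statistics by treatment and time point, and a count: "the number of patients with values above key threshold values will be displayed". It gives no values for these thresholds.

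SAP 8.2 (ECG evaluations) gives them. It says that the frequency of "patients with the following abnormalities will be displayed" and lists seven rows:

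- QRS above 120 ms, and QRS rise above 25%
- QTcF above 500 ms, and "QTcF increase from baseline > 60 ms"
- heart rate below 30 bpm, a fall of 25% or more, and heart rate above 130 bpm

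Protocol 4.2, criterion 8, excludes patients with PR above 200 ms, "QRS complex > 120 msec", or QTcF above 450 ms (men) or 460 ms (women) at screening or baseline. Protocol 8.6.7 includes PR among the intervals recorded.

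SAP Section 2 lists, among the first interpretable results, "Number and percentage of subjects with ECG abnormalities, by treatment group and time point". It gives this once for Parts 1 and 2 to Day 90 and once for the Part 2 patients on 180 days of treatment.

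Protocol 3.6.2.5 gives the reason for watching ECGs: "Small QTc effects were observed at high doses and exposures in nonhuman primates". The same paragraph adds that no other species showed this and that the human risk is thought small, and it promises close ECG monitoring.

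**The concern.** The frequency table is the only planned ECG display that says how many patients in each arm crossed a limit. Its QTcF rows sit well above the level at which the protocol already treats an ECG as abnormal enough to bar entry, and PR is missing.

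The SAP is also uneven. The QRS row equals its entry limit, and the vital-sign ranges in the same section match inclusion criterion 11. QTcF and PR are not handled this way.

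With about 20 patients per arm, few or none may reach the two QTcF rows even if a dose affects some patients moderately. What is at stake is the ability to compare LNP023 with placebo on the number of moderate QTcF and PR changes. No efficacy result depends on it.

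**Working it through.** **Step 1. Entry limits against table rows.** The documents give no figure to reproduce, so the lists are set side by side.

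| Interval | Entry limit (Protocol 4.2) | Absolute row (SAP 8.2) | Change row (SAP 8.2) |
|---|---|---|---|
| QRS | > 120 ms | > 120 ms | rise > 25% |
| QTcF | > 450 ms men, > 460 ms women | > 500 ms | rise > 60 ms |
| PR | > 200 ms | none | none |

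Of the three intervals with an entry limit, one has a matching row.

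**Step 2. Which QTcF values fall in no row.** An on-drug value x from baseline b is missed when x ≤ 500 and x − b ≤ 60. Take b at or below the entry limit.

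- Men, x = 451: missed for b from 391 to 450; counted for b below 391.
- Men, x = 500: missed for b from 440 to 450; counted for b below 440.
- Women, x = 461: missed for b from 401 to 460.
- Women, x = 500: missed for b from 440 to 460.

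A man going from 445 to 495 ms (+50 ms) is in no row. A man going from 385 to 451 ms (+66 ms) is counted. A patient starting at the entry limit needs a rise of more than 500 − 450 = 50 ms (men) or 500 − 460 = 40 ms (women) to reach the absolute row.

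**Step 3. PR.** With no row, every PR above 200 ms is missed, for example a change from 190 to 250 ms.

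**Step 4. Arm sizes.** About 48 + 50 = 98 patients over five arms, with roughly equal overall allocation intended, gives about 20 per arm. Part 1 already places 14 on 200 mg, so the Part 2 table holds only about 20 − 14 = 6 patients on that dose.

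**Step 5. Per-visit tail probabilities.** The documents give no SD for QTcF change. Assumptions: normal changes, SD 12, 17 or 22 ms, true mean shift 0, 10 or 20 ms. P(change > c) = 1 − Φ((c − shift)/SD).

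| Shift | P(rise > 30 ms), SD 12 / 17 / 22 | P(rise > 60 ms), SD 12 / 17 / 22 |
|---|---|---|
| 0 | 0.006 / 0.039 / 0.086 | < 0.001 / < 0.001 / 0.003 |
| 10 | 0.048 / 0.120 / 0.182 | < 0.001 / 0.002 / 0.012 |
| 20 | 0.202 / 0.278 / 0.325 | < 0.001 / 0.009 / 0.035 |

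In 20 patients at one visit with a shift of 10 to 20 ms, the expected number above +60 ms is 0 to 0.7 (20 × 0.035). Above +30 ms it is 1 to 6.5 (20 × 0.048 to 20 × 0.325), against 0.1 to 1.7 with no shift.

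**Step 6. Any-time counts.** The Part 2 schedule shows eight ECGs after the first dose. If changes were independent across these times, P(ever) = 1 − (1 − p)^8. This is an upper bound, because all changes share one baseline.

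- Rise > 60 ms, shift 20, SD 22: 1 − (1 − 0.0345)^8 ≈ 0.25.
- Rise > 30 ms, no shift: 0.05 at SD 12 (p = 0.0062) to 0.51 at SD 22 (p = 0.0863).

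The step 5 figures therefore cannot be read as any-time figures.

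**The case against.** **These patients do not vanish.** A reader might infer that a patient who passes an entry limit on drug is counted nowhere. The documents do not support that. A rise above 60 ms or a value above 500 ms has a row. All ECG data are listed with abnormalities flagged (SAP 8.2), individual profiles are plotted (SAP 8.3), and clinically significant findings go to the AE form (Protocol 8.6.7) and so into the AE tables. This stands. But SAP 8.2 sets no flag limits for ECGs beyond its seven rows, plots give no n or percentage, and the AE route depends on the investigator's judgement.

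**A mean shift is covered.** A reader might also infer that the ECG analysis as a whole gives false reassurance. It does not follow. SAP Section 2 plans mean QTcF over time, SAP Section 3 plans mean change from baseline by arm at IA2, and SAP 8.2 plans summary statistics by visit. With 20 per arm and SD 12 to 22 ms, the standard error of a difference is SD × √(2/20) = 3.8 to 7.0 ms. A 20 ms shift is then 2.9 to 5.3 standard errors, and a 10 ms shift 1.4 to 2.6. This stands too. What these displays do not give is the number of patients affected.

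**Nothing ties the key thresholds to the entry limits.** Correct. Eligibility limits serve another purpose, and the QRS match creates no rule.

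**The prior signal is weak.** Protocol 3.6.2.5 reports no PR finding, and Protocol 3.6.2 reports no ECG change on Holter monitoring in the first-in-human trial. This supports a low priority.

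**A per-patient count is not ruled out.** SAP 8.2 attaches visit and time point to the summary statistics, and only the first interpretable results are expressly by time point. Fair, but no any-time count is stated either.

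**Conclusion.** The gap is confirmed by reading the two lists together. The ECG frequency table omits QTcF above 450 ms (men) or 460 ms (women) up to 500 ms when the rise is 60 ms or less, and every PR above 200 ms. It is a shortfall in one safety display, of low severity; the primary analysis is unaffected.

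The omission itself rests on no assumption beyond treating the SAP list as complete, which is how it is written. The baseline ranges in step 2 assume that baseline does not exceed the entry limit; the SAP takes the last pre-dose value, which may be later than the eligibility ECG. The tail probabilities are per-visit illustrations under assumed SDs and shifts. They show that the rise-above-60 row would seldom separate arms of 20 at one visit, and they say nothing firm about any-time counts.

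**What to change.** In the ECG list of SAP 8.2, keep all seven rows and add:

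- QTcF above 450 ms (men) and above 460 ms (women)
- PR above 200 ms

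Intermediate rows for QTcF above 480 ms and a rise above 30 ms are optional. Neither document contains them, so they are suggestions only.

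In SAP 8.2 and in the matching outputs of SAP Section 2, report each row by arm in two ways: patients with the abnormality at any post-baseline time, each counted once, and patients by time point.

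The cost is SAP and table-shell wording and a few rows from ECGs already collected. No assessment or clinical rule changes. The downside is noise: lower limits will catch random excursions in every arm, and the any-time count more of them (step 6), so the rows should be read against placebo.
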